RCT. The final phase of the proposed project will implement an RCT to examine whether the program is feasible and associated with improvements in the treatment targets (see Measures and Figure 1). Thirty-six siblings will be recruited and randomly assigned to participate in Siblings FORWARD (N=18) or receive written materials about future planning (N=18). Siblings assigned to Siblings FORWARD will complete Time 1 (pre-program) measures, participate in the 6-session intervention over 4 months, complete Time 2 measures immediately after program completion, and complete Time 3 measures 3 months later. Those assigned to the control condition will complete Time 1 measures at the time of enrollment, Time 2 measures 4 months after enrollment, and Time 3 measures 7 months after enrollment. With the exception of the clinician rating of the sibling's ASD symptoms (see Measures), all data will be collected by the Boston University study team via home visits in order to separate data collection from the Arc providers. Adults with ADS and their families will determine whether the adult with ASD can complete the questionnaires (see Methods). When possible, the adult with ASD will complete the measures independently in the presence of a Boston University research team member. These measures can also be completed with the support of a research team member, sibling, parent, or service provider. Given possible geographic separation, sibling data will be collected via mailed questionnaire packets. We will track this data collection method to inform future data collection logistics.

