**Control Condition.** Currently, the standard of care is minimal sibling involvement in future planning or therapeutic activities for their brother/sister with ASD. Some organizations have created resources targeted toward parents (e.g., the Arc's Build Your Plan™ tool), but our preliminary data show that these resources are often perceived by siblings to be minimally helpful and/or overwhelming, which serves to increase their anxiety and decrease the likelihood that they will take action. Several organizations have recently published "tip sheets" for siblings who wish to have a larger role in future planning. The extent to which these tip sheets are accessed by siblings or helpful as standalone resources is unknown, but they are frequently the only resource available to siblings. Given that tip sheets are inexpensive and easy to create and disseminate, it will be important for the proposed project to demonstrate that the outcomes of the Siblings FORWARD program warrant the extra time and resources. Therefore, the control condition will involve providing the same tip sheets and packet of information about resources for adults with ASD as those distributed in Session 3 of the Siblings FORWARD program. After all outcome data are collected from the program and control groups, siblings in the control condition will be offered the opportunity to participate in the Siblings FORWARD program.

**Telehealth Technology. Rationale:** The Siblings FORWARD program will be delivered via synchronous videoteleconferencing (VTC) technology. VTC technology enables the secure delivery of interactive meetings that incorporate audio and video streams of data across multiple sites. The considerable growth of VTC interventions over the last few years has been bolstered by technological advances in VTC, portability of the technology, decreased costs, and increased internet access and technological literacy of the general population. This approach has been employed to overcome geographical barriers to care, which has led to increased availability, accessibility, and acceptability of mental health care delivered remotely. Although most telehealth research focuses on individuals, recent work supports the feasibility of family-based telehealth.

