*Aim 3: To assess the outcomes of participation in the Siblings FORWARD program.* We will examine whether the program shows promise of being successful with the intended population by conducting two-way repeated measures ANOVAs examining main effects of intervention condition (Siblings FORWARD vs. control) and repeated for assessment (pre- post- and 3-month follow up) on measures for program targets (sibling problem solving skills, family communication, future planning self-efficacy, barriers to future planning, and knowledge of services and family future plans) and proximal outcomes (sibling plan of action and adult with ASD quality of life, perceptions of unmet needs, and family relationships). Post-hoc tests will be used in multiple comparisons between groups and within each group. Effect sizes (Cohen's d) will be calculated using the mean difference of the changes recorded from pre- to post-program. We will also analyze percent change and reliable change. If data are missing, analyses will be performed using the 'last observation carried forward' method for intention-to-treat analysis. We will examine descriptive statistics (mean, SD, confidence intervals) at the participant level for patterns and direction of change on outcome measures. We will conduct intent-to-treat analyses if there is program attrition. Finally, we will examine benefit of the program to control participants who elect to participate in the Siblings FORWARD program using one-way ANOVAs (pre to post-program) on treatment targets and proximal outcomes.

We will conduct a preliminary investigation of potential moderators of program effectiveness, including characteristics of the sibling (BAP), family (income, race/ethnicity, English as the primary language, number of family members with ASD), and adult with ASD (severity of ASD symptoms, problem behaviors, functional independence). We will calculate correlations between these variables and change scores in primary outcome variables, and independent samples t-tests between these variables and program completion status.

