**Table 4: Timeline & Milestones**

Table 4: Timeline & Milestones		
Y1	Jan-Mar	
 
- Convene CAB to review qualitative goals
 
- Hire & train staff
 
- Finalize recruitment procedures
 

	Apr-June	
 
- Recruit & conduct focus groups/interviews with service providers (N=12-16), siblings (N=18-24), & adults with ASD (N=8)
 
- Analyze qualitative findings
 
- Finalize program manual by incorporating qualitative findings & CAB input
 
- Set up WebEx technology
 

	July-Dec	
 
- Provide in-depth training on program delivery to providers
 
- Conduct open trial (N=5)
 
- Provide ongoing, intensive consultation to community providers
 
- Collect, analyze, & iteratively implement feasibility & acceptability data from open trial participants & providers
 

Y2	Jan-Dec	
 
- Implement the RCT by enrolling ~2 families per month (24 siblings)
 
- Prepare conference papers & manuscripts from qualitative data
 

Y3	Jan-June	
 
- Continue RCT by enrolling ~2 families per month (12 additional siblings)
 

	July-Sept	
 
- Finish collecting 3-month follow-up data
 
- Offer Siblings FORWARD program to control siblings
 

	Oct-Dec	
 
- Collect post-program data for control sibs who later enrolled in Siblings FORWARD
 
- Conduct quantitative & qualitative analyses from RCT
 
- Revise and finalize program manual
 
- Prepare conference papers & manuscripts
 
- Prepare grant application for a larger-scale trial of the program
 

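### The pre-to-post analysis of control siblings who later take the program has no defined or scheduled baseline, so elapsed time is mixed into the change

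*Combined protocol and SAP*

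**What the plan says.** Data Analysis, Aim 3, ends its account of the outcome analyses with a look at "benefit of the program to control participants who elect to participate in the Siblings FORWARD program". The stated method is a within-group comparison, "using one-way ANOVAs (pre to post-program) on treatment targets and proximal outcomes".

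Under Procedures (RCT), the control arm's assessments are fixed by enrollment date: "Those assigned to the control condition will complete Time 1 measures at the time of enrollment, Time 2 measures 4 months after enrollment", then "Time 3 measures 7 months after enrollment". The pre-program label is tied to a numbered occasion only for the other arm: "Siblings assigned to Siblings FORWARD will complete Time 1 (pre-program) measures".

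The Control Condition paragraph of the program description sets the order of events: "After all outcome data are collected from the program and control groups, siblings in the control condition will be offered the opportunity to participate". Table 4 enrolls about two families a month through Y2 (24 siblings) and January to June of Y3 (12 more). It places the offer to controls in July to September of Y3 and then, in October to December, lists "Collect post-program data for control sibs who later enrolled in Siblings FORWARD". It lists no matching collection before these siblings start.

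**The concern.** A pre-to-post change can be read as a program effect only if the first measurement is close to the start of the program. Here the only measurements described before the delayed program are the control-period Times 1 to 3, which follow each sibling's enrollment date and not the date of the first delayed session. For a sibling enrolled early, most of the measured interval would fall before the program began.

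Several targets could move in that time without the program: how much the family has discussed the future, what the sibling knows about services, and what the sibling knows of the family's plans. With no concurrent comparison group, any such movement would be counted as benefit. The age of the baseline also differs between siblings, so the average change has no single meaning.

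**Working it through.** **Inputs.** Enrollment of about 2 a month from Y2 January to Y3 June, and the offer in Y3 July to September (Table 4). Control assessments at 0, 4 and 7 months (Procedures). A 4-month program (program description). 18 controls (Procedures).

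**Reproducing the plan's figure.** 2 × 12 = 24 and 2 × 6 = 12, total 36, as stated.

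**Assumptions.** Monthly steps, even enrollment, arms spread evenly over time, program start in the month of the offer. Months are numbered from Y2 January = 1, so the last enrollment month is 18, Y3 July is 19 and Y3 September is 21.

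**Age of the baseline at program start.** For enrollment in month e and program start in month s:

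- Time 1 age = s − e
- Time 3 age = s − (e + 7)

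The last Time 3 falls in month 18 + 7 = 25, which is Y4 January. That is the earliest start if the offer waits for all outcome data.

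| Delayed start | Time 1 age, first enrollee | Time 1 age, mean (s − 9.5) | Time 3 age, first enrollee | Time 3 age, mean of those who have it | Siblings (of 36) without Time 3 by then |
|---|---|---|---|---|---|
| Y3 July (19) | 19 − 1 = 18 | 9.5 | 19 − 8 = 11 | 5.5 | 2 × (18 − 12) = 12 |
| Y3 Sept (21) | 21 − 1 = 20 | 11.5 | 21 − 8 = 13 | 6.5 | 2 × (18 − 14) = 8 |
| Y4 Jan (25) | 25 − 1 = 24 | 15.5 | 25 − 8 = 17 | 8.5 | 0 |

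Half of the last column would be controls: about 6 for a July start and 4 for a September start.

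For the first enrollee on Table 4's calendar, the whole interval to the post-program score is 18 + 4 = 22 to 20 + 4 = 24 months from Time 1, or 11 + 4 = 15 to 13 + 4 = 17 months from Time 3. Four of those months are the program.

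**What falls inside the change.**

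- From Time 1: the tip sheets and packet, the plan of action written at Time 2, elapsed time, and the program.
- From Time 3: elapsed time and the program. Receipt of the materials and the Time 2 exercise come before this baseline, so only delayed effects of them remain.

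**Which outcomes each occasion can supply.** The Measures section collects the program targets at Times 1, 2 and 3, the plan of action at Time 2 (with goal attainment checked at follow-up), and quality of life at Times 1 and 3. It gives no timing for unmet needs or family relationships. No single control-period occasion supplies both the plan of action and quality of life, yet the analysis is stated for treatment targets and proximal outcomes together.

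**Calendar conflict.** Table 4 finishes the 3-month follow-up and makes the offer by September of Y3 (month 21), but the last Time 3 falls in month 25. The offer in Table 4 therefore comes before all outcome data are in, contrary to the Control Condition paragraph. If the offer does wait until month 25, post-program scores come no earlier than month 25 + 4 = 29, beyond the end of Table 4 (Y3 December, month 24).

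**The case against.** Table 4 is a list of milestones, not a schedule of assessments. It has no row for Time 1 or Time 2 in either arm, although both are planned, so its silence does not prove that no pre-program measurement is intended. The Aim 3 wording implies that some earlier score will be used. This stands. What can be shown is that the baseline is undefined and that no section describes a fresh one.

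A reader might infer that the change spans about 18 months and also contains the materials and the Time 2 exercise. On Table 4's calendar both are true only if the baseline is Time 1. With Time 3 the gap is 11 to 13 months at most and those two exposures mostly drop out. The two baselines should not be combined into one claim. The longest Time 3 gap, about 17 months, arises only if the offer waits for all outcome data, which Table 4's calendar does not allow.

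A reader might also infer that planning is bound to drift upward. The documents do not show this. Preliminary Studies reports more sibling involvement when the mother's health was declining, which is an association and not a rate of change. The Control Condition paragraph describes minimal sibling involvement as the norm. The family-plan checklist records what the sibling knows, not whether a will or trust has been set up. Drift is plausible, but neither its direction nor its size is documented.

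Finally, this is a secondary analysis of at most 18 volunteers in a pilot, and any single-group change is confounded with time. A fresh baseline shortens the interval but does not remove that confounding. This also stands, and it limits what the fix can claim.

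**Conclusion.** The point holds for the analysis of crossed-over controls. As written, its baseline is undefined, and every occasion on offer is old for early enrollees:

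- Time 3: up to 11 to 13 months at program start on Table 4's calendar, or about 17 if the offer waits for all outcome data. On Table 4's calendar the latest enrollees have no Time 3 score by then.
- Time 1: up to 18 to 20 months, or about 24, with the control-period exposures added.

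These are maxima. The means are 5.5 to 6.5 months (Time 3, among those who have it) and 9.5 to 11.5 months (Time 1) on Table 4's calendar. All rest on the enrollment and start-date assumptions listed above. Against a 4-month program, such gaps are enough to make the change uninterpretable as program benefit.

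The randomized comparison is untouched, and the documents do not support a claim that the result would be biased in a known direction. This is a worthwhile, inexpensive improvement to a secondary analysis.

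**What to change.** - **Add a baseline.** In Aim 3 and Table 4, add one mailed packet of the sibling-reported program-target measures shortly before the first delayed session, and define it as the baseline. Procedures already uses mailed packets for sibling data. This gives every crossover sibling the same interval, roughly the 4-month program.
- **Restrict the outcomes.** Leave the plan of action out of this analysis, because these siblings already completed it at Time 2. Also leave out any proximal outcome not re-measured at the new baseline.
- **Label the result.** Report it as descriptive and uncontrolled, applying to siblings already exposed to the written materials. The same siblings' Time 1 to Time 2 change may be shown alongside as a 4-month reference, with a note that it includes receipt of those materials and so is not a pure untreated course.
- **Reconcile the calendar.** Bring the offer timing in the Control Condition paragraph and in Table 4 into agreement.

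Cost: one extra questionnaire for at most 18 siblings, with the added burden on them, and a few sentences in Aim 3 and Table 4.
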